At treatment visits (Visits 2, 4 & 6), subjects will provide details of their concomitant medications and undergo an OST examination. Subject's diaries will be reviewed to ensure compliance with the use of the wash-out dentifrice. Subjects deemed suitable to continue in the study will be randomized to the order of treatments (Visit 2 only) and wear an oral palatal appliance holding 8 bovine enamel specimens. Details of enamel specimen preparation will be specified in the Laboratory Procedures Document. The palatal appliances (Fig 4-1) will be specifically made for each eligible subject, and each will carry two plastic holders containing a total of eight bovine enamel specimens (four in each holder). Once the appliance is fitted in the mouth, a five minute equilibration period will ensue following which each subject will brush their teeth with their assigned product, one product per treatment visit as described below.

[figure not shown]

Figure 4-1 Schematic diagram of a) intraoral appliance, b) enamel specimens' holder, c) enamel specimens placed in the holder and d) palatal appliance with enamel specimens in the mouth.

Under supervision while the intraoral appliance is in place, the subjects will brush the buccal surfaces of their natural teeth using 1.5 ± 0.1 g of dentifrice and a soft toothbrush for 25 seconds to create a slurry. Subjects will be instructed not to expectorate the slurry and will then swish the slurry around their mouth for 95 seconds to permit direct contact of the dentifrice slurry with the enamel specimens. After expectorating the slurry, the subjects will gently rinse their mouths with 15 mL of tap water for 10 seconds before expectorating again. The toothbrush, however, will not come into contact with the enamel specimens or the appliance as this could cause abrasion of the enamel specimens.

Subjects will then remain at the study site for 4 hours post toothbrushing when their appliance will be removed (at $4\text{hrs} \pm 10$ mins post toothbrushing) and 4 designated enamel specimens will be withdrawn from the appliance. Subjects will then be served an optional lunch which will be consumed within a 30 ± 10 minute time period. The subjects will then brush and rinse their

Property of Haleon- Confidential

May not be used, divulged, published or otherwise disclosed without the consent of Haleon

mouth with water, after which they will have their appliance reinserted and be allowed to leave the site.

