8.1.9 Dispense Wash-out Products and Diary Cards

Subjects will be dispensed with the washout toothbrush and the 0ppm fluoride washout dentifrice to use during the washout period. Subjects will be instructed to brush their teeth with the 0ppm fluoride washout dentifrice twice a day during the 2 days prior to Visit 2, 4 and 6 (including the morning of the treatment visit) and record it in the diary provided.

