10.1 Definition of an Adverse Event (AE)

An AE is any untoward medical occurrence in a clinical study subject, temporally associated with the use of a study product including any washout or lead-in product (or medical device), whether or not considered related to the study product, including any washout or lead-in product (or medical device).

NOTE: An AE can therefore be any unfavorable and unintended sign (including an abnormal laboratory finding), symptom, or disease (new or exacerbated) temporally associated with the use of a study product including any washout or lead-in product (or medical device).

Events Meeting the AE Definition:

Property of Haleon- Confidential

May not be used, divulged, published or otherwise disclosed without the consent of Haleon

- Any abnormal laboratory test results (hematology, clinical chemistry, or urinalysis) or other safety assessments (e.g. ECG, radiological scans, vital sign measurements), including those that worsen from baseline, considered clinically significant in the medical and scientific judgment of the investigator (i.e., not related to progression of underlying disease).
- Exacerbation of a chronic or intermittent pre-existing condition including either an increase in frequency and/or intensity of the condition.
- New conditions detected or diagnosed after study product administration even though it may have been present before the start of the study.
- Signs, symptoms, or the clinical sequelae of a suspected drug-drug interaction.
- Signs, symptoms, or the clinical sequelae of a suspected overdose of either study product or a concomitant medication. Overdose per se will not be reported as an AE/SAE unless it is an intentional overdose taken with possible suicidal/self-harming intent. Such overdoses should be reported regardless of sequelae.
- "Lack of efficacy" or "failure of expected pharmacological action" per se will not be reported as an AE. Such instances will be captured in the efficacy assessments. However, the signs, symptoms, and/or clinical sequelae resulting from lack of efficacy will be reported as AE if they fulfill the definition of an AE.

Events NOT meeting the AE definition:

- Any clinically significant abnormal laboratory findings (if applicable) or other abnormal safety assessments which are associated with the underlying disease, unless judged by the investigator to be more severe than expected for the subject's condition.

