12.3.4 Safety Analyses

AEs will be regarded as treatment emergent if they occur on or after the first use of study product in the study. In this crossover trial, events will be assigned to the study product being received at the onset of the event. Treatment-emergent adverse events (TEAEs) with an onset date/time between visits will be assigned to the study product received in the previous period. TEAEs with an onset after last use of any study product will be assigned to the last study product used.

The number of distinct events and the number and percentage of subjects having at least one event will be presented by study product and overall for the following:

- AEs (overall only)
- SAEs (overall only)
- TEAEs
- Serious TEAEs
- Oral TEAEs
- Product Related TEAEs
- Device related AEs
- Device Incidents

All AEs and device incidents will be listed providing all relevant details collected in the CRF.

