4.1.3 Analysis Populations

The following analysis populations will be defined:

- The Screened population will include all subjects who are screened.
- The Intent-to-Treat (ITT) population will include all subjects who are randomized. Study product group will be assigned to each visit for analyses based on the study product sequence the subject was randomized to.
- The Safety population will include all randomized subjects who receive at least 1 dose of study product. Study product group will be assigned for analyses based on the last known study product the subject actually received prior to the safety event.
- The Per-Protocol (PP) population will include all subjects from the ITT population who have at least one visit with non-missing erosion parameters unaffected by protocol deviations. Study product group will be assigned to each visit for analyses based on the study product the subject received.

Subjects excluded from any of the ITT, Safety and PP analysis populations will be listed for all subjects in the Screened population in Listing 16.2.3, with the reason for exclusion.

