4.5 Analysis of Safety

AEs will be regarded as treatment emergent if they occur on or after the date of first use of study product in the study. In this crossover trial, events will be assigned to the study product being received at the onset of the event. Treatment-emergent adverse events (TEAEs) with an onset date/time between visits will be assigned to the study product received in the previous period. TEAEs with an onset after last use of any study product will be assigned to the last study product used.

The number of distinct events and the number and percentage of subjects having at least one event will be presented by study product and overall for the following:

- AEs (overall only)
- SAEs (overall only)
- TEAEs
- Serious TEAEs
- Oral TEAEs
- Product Related TEAEs
- Device related AEs
- Device Incidents

All AEs and device incidents will be listed providing all relevant details collected in the CRF.

5 Changes to the Protocol Defined Statistical Analysis Plan

There were no changes or deviations to the originally planned statistical analysis specified in the protocol/protocol amendment (Dated: DD/MMM/YYYY).

<Compound/Product>

<Protocol Number>

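### Oral events that start during the washout before Visits 4 and 6 are counted under the previous study product and cannot be told apart in Table 14.3.1

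*SAP*

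**What the plan says.** **Attribution.** SAP 4.5 states: "Treatment-emergent adverse events (TEAEs) with an onset date/time between visits will be assigned to the study product received in the previous period". Protocol 12.3.4 uses the same words. The Safety population definition in SAP 4.1.3 points the same way, assigning product "based on the last known study product the subject actually received prior to the safety event".

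**Start of treatment emergence.** SAP 4.5: "AEs will be regarded as treatment emergent if they occur on or after the date of first use of study product in the study". No later cut-off is given, and no category is set aside for washout.

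**Exposure.** At a treatment visit "each subject will brush their teeth with their assigned product, one product per treatment visit as described below" (Protocol 4.1). Subjects are also to use the "0ppm fluoride washout dentifrice twice a day during the 2 days prior to Visit 2, 4 and 6" (Protocol 8.1.9), with the visit morning included. Protocol 8.2 adds at least one day on the subject's own dentifrice before that, and at least 3 days between doses, with no maximum.

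**Washout reactions are adverse events.** Protocol 10.1 covers any untoward occurrence "temporally associated with the use of a study product including any washout or lead-in product (or medical device".

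**Reporting.** Table 14.3.1 has columns for Test, Reference, Placebo and Overall. Listing 16.2.7.1 shows visit dates, event dates and the last study product used. It has no washout dates and no washout flag.

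**The concern.** The only safety objective is the oral tolerability of the experimental dentifrice, and its endpoint is TEAEs. In periods 1 and 2, the window booked to a study product contains one use of that product, then the subject's own dentifrice, then a sponsor-supplied washout dentifrice used several times.

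The soft tissue examination at Visits 4 and 6 is done before the appliance goes in, so directly after the washout days. Under Protocol 9.3.1 any new abnormality is an adverse event. Such a finding is reported under whichever product the sequence placed in the preceding period.

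A reader of Table 14.3.1 would take the oral TEAE percentage for Test as a rate for Test. Part of it may belong to something else, and the table gives no way to see how much.

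**Working it through.** The plan states no adverse event rate or precision for safety, so there is no safety figure to reproduce. Its power figures concern %SMHR and %RER and do not bear on this point.

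**1. Where a washout-onset event goes.** Take a soft-tissue reaction that starts on the day before Visit 4.
- It is an adverse event (Protocol 10.1).
- It is treatment emergent, because it falls after first study-product use at Visit 2.
- It falls between visits, so it is assigned to the period 1 product. If it is first seen at the Visit 4 examination, the last-product-received rule in SAP 4.1.3 gives the same result.
- In Table 14.3.1 it is a TEAE and an oral TEAE of that product.

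**2. Exposure inside the window.** The study product is used once. The washout is used twice daily for two days: 2 x 2 = 4 brushings if the visit morning is counted within them, 4 + 1 = 5 if it is extra. At the minimum 3-day interval the washout covers 2 of the 3 days. A longer interval adds days on the subject's own dentifrice. It lowers the washout's share of the time but not the number of washout brushings.

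**3. Share of periods affected.** A washout follows periods 1 and 2 but not period 3. Over the six sequences each product is in period 1 twice, period 2 twice and period 3 twice, so 4/6 = 2/3 of its periods are followed by a washout. With 30 balanced completers that is 20 of 30 per product. With 33 (five full blocks plus three sequences of a sixth) it is 20 + 1 to 20 + 3, or 21-23 of 33.

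**4. Size, for illustration only.** Let p be the oral event risk from one study-product use and w the risk from one washout course. Both are assumed, and taken as independent with w the same after every product.

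Booked risk = (2/3)[1 - (1 - p)(1 - w)] + (1/3)p = p + (2/3)w(1 - p)

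Example: p = 2%, w = 5% gives 0.02 + (2/3)(0.05)(0.98) = 0.0527, or 1.58 of 30 subjects, against 0.60 from the product alone.

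| Expected subjects of 30 | Product alone | w = 1% | w = 5% | w = 10% |
|---|---|---|---|---|
| p = 0% | 0 | 0.20 | 1.00 | 2.00 |
| p = 2% | 0.60 | 0.80 | 1.58 | 2.56 |
| p = 5% | 1.50 | 1.69 | 2.45 | 3.40 |

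At p = 2%, the washout makes up 25% (w = 1%) to 77% (w = 10%) of the booked risk. At p = 5% it makes up 11% to 56%.

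**5. Comparison between products.** From the formula, booked difference = (p1 - p2)(1 - 2w/3). For an assumed 6% against 2%, a true difference of 4.0 points becomes 3.9 at w = 5% and 3.7 at w = 10%. The true ratio of 3.0 becomes 0.0913/0.0527 = 1.73 and 0.1227/0.0853 = 1.44.

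**The case against.** The strongest reply is that this is a prespecified convention, stated alike in both documents, and a conservative one: a doubtful event counts against a study product. That stands, and it is a good reason to keep the rule for the main display.

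It can also be said that much is already recoverable. Protocol 10.5.2 requires a causality assessment that weighs timing and alternative causes. Product-related TEAEs are tabulated by product. With at most 33 subjects, the dates in Listing 16.2.7.1 let a reader place most washout-period onsets by hand. This stands in part. Protocol 10.1 counts the washout within study product, so related may itself include related to the washout, and hand recovery from a listing does not help a reader of the table.

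Three stronger readings are tempting, and the documents do not support them.
- *That the rule hides real differences between products.* The Williams sequences load the three columns about equally, no between-product test of adverse events is planned, and step 5 shows the risk difference barely moving. Only a ratio would be diluted, and no ratio is planned.
- *That washout-onset events should leave the product columns.* At the minimum interval this would cut the attribution window in periods 1 and 2 to about one day, while Protocol 10.3 collects events for 5 days after the last use in period 3. Late reactions, and examination findings of unknown onset, could leave the Test column, which is anti-conservative for the stated objective.
- *That a reaction in the first washout is never treatment emergent.* SAP 4.5 works by date, so a reaction on the morning of Visit 2 would count. Protocol 12.3.4 works from first use, so it would not.

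**Conclusion.** The point holds as one of reporting. The text alone shows that oral events starting in the washout before Visits 4 and 6 are counted as TEAEs and oral TEAEs of a study product used once, days before, and that Table 14.3.1 cannot separate them. About two thirds of each product's periods carry this window.

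The direction is upward for each product's absolute rate. The amount cannot be estimated from the documents: the figures in step 4 rest wholly on assumed p and w, and a very low washout event rate would make the effect negligible. The equal loading of the columns depends on the sequences staying balanced.

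A reader might infer that every column mixes two different formulations. For Placebo this cannot be established: Table 6-2 describes the washout in the same terms as the placebo (0 ppm fluoride, 5% KNO3), but the formulation codes are redacted. If the two are alike, Placebo is affected least, although its count would still reflect the extra brushings.

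**What to change.** Keep the current attribution in Protocol 12.3.4 and SAP 4.5 as the main display, and add the following to the SAP:

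1. In Table 14.3.1, under TEAEs and under oral TEAEs, a sub-count by product and overall of events with onset during the washout. The window runs from the first washout brushing recorded in the diary until the next study-product use. If that brushing date is not in the database, start the window two days before the next treatment visit.
2. A flag for these events in Listing 16.2.7.1.
3. A rule that soft tissue findings of unknown onset stay with the previous product and are flagged as first seen after washout.
4. A statement of whether product-related includes relatedness to the washout dentifrice.

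**Cost.** A few table rows and one derived flag. Protocol 6.7 requires only missed or additional washout applications to be transcribed to the CRF, so the first-brushing date may not be available; the two-day fallback avoids new data capture. A late reaction to a study product may carry the washout flag, but it stays in that product's column.

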Appendix 4: List of Data Displays

Type	Number	Title	Population	Topline Output
Tables and Figures				
14.1 Demographic Data Summary figures and tables.				
Table	14.1.1	Subject Disposition by Treatment Group Across Study Treatment Periods	ITT Population	
Table	14.1.2	Subject Disposition by Sequence Group and Period	ITT Population	
Table	14.1.3	Incidence of Important Protocol Deviations	ITT Population	
Table	14.1.4.1	Demographic Characteristics	Safety Population	
Table	14.1.4.2	Demographic Characteristics	ITT Population	
Table	14.1.4.3	Demographic Characteristics	PP Population	
14.2 Objectives Data Summary figures and tables.				
Table	14.2.1.1.1	Statistical Analysis of Surface Microhardness Recovery (%SMHR) at 4 Hours by Treatment Group	ITT Population	Yes
Table	14.2.1.1.2	Statistical Analysis of Surface Microhardness Recovery (%SMHR) at 4 Hours by Treatment Group	PP Population	Yes
Table	14.2.1.2.1	Statistical Analysis of Surface Microhardness Recovery (%SMHR) at 12 Hours by Treatment Group	ITT Population	Yes
Table	14.2.1.2.2	Statistical Analysis of Surface Microhardness Recovery (%SMHR) at 12 Hours by Treatment Group	PP Population	Yes

Haleon Confidential

SOP-208559 Statistical Analysis Plan template v7.0

Page 20 of 43

Figure	14.2.1.3	Bar Chart with Error Bars (\pm SE) for Adjusted Mean Surface Microhardness Recovery (%SMHR) at 4 and 12 hours	ITT Population	
Table	14.2.2.1.1	Statistical Analysis of Relative Erosion Resistance (%RER) at 4 Hours by Treatment Group	ITT Population	Yes
Table	14.2.2.1.2	Statistical Analysis of % Relative Erosion Resistance (%RER) at 4 Hours by Treatment Group	PP Population	Yes
Table	14.2.2.2.1	Statistical Analysis of % Relative Erosion Resistance (%RER) at 12 Hours by Treatment Group	ITT Population	Yes
Table	14.2.2.2.2	Statistical Analysis of % Relative Erosion Resistance (%RER) at 12 Hours by Treatment Group	PP Population	Yes
Figure	14.2.2.3	Bar Chart with Error Bars (\pm SE) for Adjusted Mean Relative Erosion Resistance (%RER) by Treatment Group	ITT Population	
Table	14.2.3.1.1	Statistical Analysis of Acid Resistance Ratio (ARR) at 4 Hours by Treatment Group	ITT Population	
Table	14.2.3.1.2	Statistical Analysis of Acid Resistance Ratio (ARR) at 4 Hours by Treatment Group	PP Population	
Table	14.2.3.2.1	Statistical Analysis of Acid Resistance Ratio (ARR) at 12 Hours by Treatment Group	ITT Population	
Table	14.2.3.2.2	Statistical Analysis of Acid Resistance Ratio (ARR) at 12 Hours by Treatment Group	PP Population	
Figure	14.2.3.3	Bar Chart with Error Bars (\pm SE) for Adjusted Mean Acid Resistance Ratio (ARR) at 4 and 12 hours	ITT Population	
Table	14.2.4	Summary Table of Indents Measures (B/E1/R/E2) by Timepoint and Treatment Group	ITT Population	
Table	14.2.5.1	Statistical Analysis of Enamel Fluoride Uptake (EFU) at 4 Hours by Treatment Group	ITT Population	
Table	14.2.5.2	Statistical Analysis of Enamel Fluoride Uptake (EFU) at 12 Hours by Treatment Group	ITT Population	
Figure	14.2.5.3	Bar Chart with 95% CI for Adjusted Geometric Mean Enamel Fluoride Uptake (EFU)	ITT Population	
14.3 Safety Data				
14.3.1 Displays of Adverse Events				

Table	14.3.1	Summary of Adverse Events and Device Incidents Overall and by Treatment Group	Safety Population	
SAS Output				
16.1.9 Documentation of statistical methods.				
SAS Output File	16.1.9.1	Statistical Analysis of Surface Microhardness Recovery (%SMHR) at 4 Hours by Treatment Group	ITT Population	Yes
SAS Output File	16.1.9.2	Statistical Analysis of Surface Microhardness Recovery (%SMHR) at 4 Hours by Treatment Group	PP Population	Yes
SAS Output File	16.1.9.3	Statistical Analysis of Surface Microhardness Recovery (%SMHR) at 12 Hours by Treatment Group	ITT Population	Yes
SAS Output File	16.1.9.4	Statistical Analysis of Surface Microhardness Recovery (%SMHR) at 12 Hours by Treatment Group	PP Population	Yes
SAS Output File	16.1.9.5	Statistical Analysis of Relative Erosion Resistance (%RER) at 4 Hours by Treatment Group	ITT Population	Yes
SAS Output File	16.1.9.6	Statistical Analysis of % Relative Erosion Resistance (%RER) at 4 Hours by Treatment Group	PP Population	Yes
SAS Output File	16.1.9.7	Statistical Analysis of % Relative Erosion Resistance (%RER) at 12 Hours by Treatment Group	ITT Population	Yes
SAS Output File	16.1.9.8	Statistical Analysis of % Relative Erosion Resistance (%RER) at 12 Hours by Treatment Group	PP Population	Yes
SAS Output File	16.1.9.9	Statistical Analysis of Acid Resistance Ratio (ARR) at 4 Hours by Treatment Group	ITT Population	
SAS Output File	16.1.9.10	Statistical Analysis of Acid Resistance Ratio (ARR) at 4 Hours by Treatment Group	PP Population	
SAS Output File	16.1.9.11	Statistical Analysis of Acid Resistance Ratio (ARR) at 12 Hours by Treatment Group	ITT Population	
SAS Output File	16.1.9.12	Statistical Analysis of Acid Resistance Ratio (ARR) at 12 Hours by Treatment Group	PP Population	

SAS Output File	16.1.9.13	Statistical Analysis of Enamel Fluoride Uptake (EFU) at 4 Hours by Treatment Group	ITT Population	
SAS Output File	16.1.9.14	Statistical Analysis of Enamel Fluoride Uptake (EFU) at 12 Hours by Treatment Group	ITT Population	
16.2 Patient Data Listings				
16.2.1 Discontinued patients.				
Listing	16.2.1	Subject Disposition	Screened Population	
16.2.2 Protocol deviations.				
Listing	16.2.2	Protocol Deviations	ITT Population	
16.2.3 Patients excluded from the efficacy analysis.				
Listing	16.2.3	Exclusions from Efficacy Analysis	ITT Population	
16.2.7 Adverse event listings				
Listing	16.2.7.1	Adverse Events	ITT Population	
Listing	16.2.7.2	Device Incidents	ITT Population	

Appendix 5: Table Shells

Each table when output from the SAS analysis program will include the program run date in the top right header and the program name in the bottom left footnote.

Table 14.1.1, Subject Disposition by Treatment Group Across Study Treatment Periods, ITT Population

Study Period		Test	Reference	Placebo	Overall
1	Randomized	N			
	Discontinued Study Prior To Visit	n (x.x%)			
	<reason n>				
	Attended Visit				
	Evaluable Erosion Data				
	<reason if not n>				
..					
3					
..					
Overall	Randomized				
	Discontinued Study Prior To Visit				
	<reason n>				
	Attended Visit				
	Evaluable Erosion Data				

Percentages are based on all subjects randomized to each specific period based on randomized sequence.

Haleon Confidential

CCI

Statistical Analysis Plan Template v7.0

Page 24 of 43

Table 14.1.2, Subject Disposition by Sequence Group and Period, ITT Population

Study Period		ABC (N=X)	ACB (N=X)	BAC (N=X)	BCA (N=X)	CAB (N=X)	CBA (N=X)	Overall (N=XX)
1	Discontinued Study Prior To Visit	n (x.x%)						
	<reason n>							
	Attended Visit							
	Evaluable Erosion Data							
	<reason if not n>							
::								
3								
::								
Overall	Completed Study							
	Discontinued Study							
	<reason n>							

A = Test, B = Reference, C= Placebo

Percentages are based on all subjects randomized within each specific sequence.

Haleon Confidential

CCI

Statistical Analysis Plan Template v7.0

Page 26 of 43

Table 14.1.3, Incidence of Important Protocol Deviations, ITT Population

	Test	Reference	Placebo	Overall (N=XXX)
Any Important Protocol Deviation	n (x.x%)			
<PD type 1>				
::				
<PD type n>				
Any Important Protocol Deviation Leading to Data Exclusion from PP analysis				
<PD type 1>				
::				
<PD type n>				

Percentages are based on all subjects randomized in the ITT population.

Haleon Confidential

CCI

Statistical Analysis Plan Template v7.0

Page 27 of 43

Table 14.1.4, Demographic Characteristics, ITT Population

		Overall (N=XXX)
Age	n, Mean (SD), Median, min-max	x, x.x (x.x), x.x, x-x
Sex	Female	n (x.x%)
	Male	n (x.x%)
Race	American Indian or Alaska Native	n (x.x%)
	Asian	n (x.x%)
	Black or African American	n (x.x%)
	Native Hawaiian or Other Pacific Islander	n (x.x%)
	White	n (x.x%)
	Multiracial	n (x.x%)
	Other	n (x.x%)
Ethnicity	Hispanic or Latino	n (x.x%)
	Not Hispanic or Latino	n (x.x%)

Percentages are based on all subjects randomized in the ITT population.

Haleon Confidential

CCI

Statistical Analysis Plan Template v7.0

Page 28 of 43

Table 14.2.1.1.1, Statistical Analysis of Surface Microhardness Recovery (%SMHR) at 4 Hours by Treatment Group, ITT Population (similar table for PP Population if necessary)

Parameter	Test	Reference	Placebo
%SMHR at 4 hours (N=XXX)			
n	x	x	x
Mean (SD, SE)	x.xx (x.xxx, x.xxx)	x.xx (x.xxx, x.xxx)	x.xx (x.xxx, x.xxx)
Median	x.xx	x.xx	x.xx
Minimum to Maximum	x.xx to x.xx	x.xx to x.xx	x.xx to x.xx
Adjusted Mean (SE, 95% CI)*	x.xx (x.xxx, x.xxx to x.xxx)	x.xx (x.xxx, x.xxx to x.xxx)	x.xx (x.xxx, x.xxx to x.xxx)
vs Placebo (SE)	x.xx (x.xxx)	x.xx (x.xxx)	
95% CI	x.xxx to x.xxx	x.xxx to x.xxx	
p-value	xxxxx	xxxxx	
vs Reference (SE)	x.xx (x.xxx)		
95% CI	x.xxx to x.xxx		
p-value	xxxxx		

*A mixed model with fixed effects for treatment and study visit, and random effect for subject.

All of the tables listed below will be similar to 14.2.1.1.1 (other than decimal places used: SMHR/RER/EFU 2 decimal places for mean, 3 for sd/se/ci; ARR 3 decimals for mean and 4 for sd/se/ci):

Table 14.2.1.2.1, Statistical Analysis of Surface Microhardness Recovery (%SMHR) at 12 Hours by Treatment Group, ITT Population (similar table for PP Population if necessary)

Table 14.2.3.1.1, Statistical Analysis of Acid Resistance Ratio (ARR) at 4 Hours by Treatment Group, ITT Population (similar table for PP Population if necessary)

Table 14.2.3.2.1, Statistical Analysis of Acid Resistance Ratio (ARR) at 12 Hours by Treatment Group, ITT Population (similar table for PP Population if necessary)

Table 14.2.2.1.1, Statistical Analysis of Relative Erosion Resistance (%RER) at 4 Hours by Treatment Group, ITT Population (similar table for PP Population if necessary); Similar table for 14.2.2.2.1, Statistical Analysis of % Relative Erosion Resistance (%RER) at 12 Hours by Treatment Group, ITT Population (similar table for PP Population if necessary)

Parameter	Test	Reference	Placebo
%RER at 4 hours (N=XXX)			
n	x	x	x
Mean (SD, SE)	x.xx (x.xxx, x.xxx)	x.xx (x.xxx, x.xxx)	x.xx (x.xxx, x.xxx)
Median	x.xx	x.xx	x.xx
Minimum to Maximum	x.xx to x.xx	x.xx to x.xx	x.xx to x.xx
Adjusted Mean (SE, 95% CI)*	x.xx (x.xxx, x.xxx to x.xxx)	x.xx (x.xxx, x.xxx to x.xxx)	x.xx (x.xxx, x.xxx to x.xxx)
vs Placebo (SE)	x.xx (x.xxx)	x.xx (x.xxx)	
95% CI	x.xxx to x.xxx	x.xxx to x.xxx	
p-value	x.xxxx	x.xxxx	
RER Ratio >= 3	x.x% (x.x% to x.x%)		
RER Ratio >=2.5 (95% CI)	x.x% (x.x% to x.x%)		
vs Reference (SE)	x.xx (x.xxx)		
95% CI	x.xxx to x.xxx		
p-value	x.xxxx		

[figure not shown]
*A mixed model with fixed effects for treatment and study visit, and random effect for subject.

Table 14.2.5.1, Statistical Analysis of Enamel Fluoride Uptake (EFU) at 4 Hours by Treatment Group, ITT Population; Similar table for 14.2.5.2, Statistical Analysis of Enamel Fluoride Uptake (EFU) at 12 Hours by Treatment Group, ITT Population

Parameter	Test	Reference	Placebo
EFU at 4 hours (ug F/cm ²) (N=XXX)			
n	x	x	x
Mean (SD, SE)	x.xx (x.xxx, x.xxx)	x.xx (x.xxx, x.xxx)	x.xx (x.xxx, x.xxx)
Median	x.xx	x.xx	x.xx
Minimum to Maximum	x.xx to x.xx	x.xx to x.xx	x.xx to x.xx
Adjusted Geometric Mean (95% CI)*	x.xx (x.xxx to x.xxx)	x.xx (x.xxx, x.xxx to x.xxx)	x.xx (x.xxx, x.xxx to x.xxx)
vs Placebo, Geometric Mean Ratio (95% CI)	x.xx (x.xxx to x.xxx)	x.xx (x.xxx to x.xxx)	
p-value	x.XXXX	x.XXXX	
vs Reference, Geometric Mean Ratio (95% CI)	x.xx (x.xxx)		
p-value	x.XXXX		

*A mixed model on log transformed EFU with fixed effects for treatment and study visit, and random effect for subject. Estimates are back-transformed.

Figure 14.2.1.3, Bar Chart with Error Bars (\pm SE) for Adjusted Mean Surface Microhardness Recovery (%SMHR) at 4 and 12 hours, ITT Population

Haleon Confidential

CCI

Statistical Analysis Plan Template v7.0

Page 33 of 43

All of the figures listed below will be similar to 14.2.1.3:

Figure 14.2.2.3, Bar Chart with Error Bars (\pm SE) for Adjusted Mean Relative Erosion Resistance (%RER) by Treatment Group, ITT Population

Figure 14.2.3.3, Bar Chart with Error Bars (\pm SE) for Adjusted Mean Acid Resistance Ratio (ARR) at 4 and 12 hours, ITT Population

Figure 14.2.5.3, Bar Chart with 95% CI for Adjusted Geometric Mean Enamel Fluoride Uptake (EFU), ITT Population

Haleon Confidential

CCI

Statistical Analysis Plan Template v7.0

Page 34 of 43

Table 14.2.4, Summary Table of Indents Measures (B/E1/R/E2) by Timepoint and Treatment Group, ITT Population

Parameter	Test	Reference	Placebo
(N=XXX)			
B at 4 hours			
n	x	x	x
Mean (SD, SE)	x.xx (x.xxx, x.xxx)	x.xx (x.xxx, x.xxx)	x.xx (x.xxx, x.xxx)
Median	x.xx	x.xx	x.xx
Minimum to Maximum	x.xx to x.xx	x.xx to x.xx	x.xx to x.xx
B at 12 hours			
n	x	x	x
Mean (SD, SE)	x.xx (x.xxx, x.xxx)	x.xx (x.xxx, x.xxx)	x.xx (x.xxx, x.xxx)
Median	x.xx	x.xx	x.xx
Minimum to Maximum	x.xx to x.xx	x.xx to x.xx	x.xx to x.xx
E1 at 4 hours			
n	x	x	x
Mean (SD, SE)	x.xx (x.xxx, x.xxx)	x.xx (x.xxx, x.xxx)	x.xx (x.xxx, x.xxx)
Median	x.xx	x.xx	x.xx
Minimum to Maximum	x.xx to x.xx	x.xx to x.xx	x.xx to x.xx
E1 at 12 hours			
n	x	x	x
Mean (SD, SE)	x.xx (x.xxx, x.xxx)	x.xx (x.xxx, x.xxx)	x.xx (x.xxx, x.xxx)

Haleon Confidential

CCI

Statistical Analysis Plan Template v7.0

Page 35 of 43

Median	x.xx	x.xx	x.xx
Minimum to Maximum	x.xx to x.xx	x.xx to x.xx	x.xx to x.xx
R at 4 hours			
n	x	x	x
Mean (SD, SE)	x.xx (x.xxx, x.xxx)	x.xx (x.xxx, x.xxx)	x.xx (x.xxx, x.xxx)
Median	x.xx	x.xx	x.xx
Minimum to Maximum	x.xx to x.xx	x.xx to x.xx	x.xx to x.xx
R at 12 hours			
n	x	x	x
Mean (SD, SE)	x.xx (x.xxx, x.xxx)	x.xx (x.xxx, x.xxx)	x.xx (x.xxx, x.xxx)
Median	x.xx	x.xx	x.xx
Minimum to Maximum	x.xx to x.xx	x.xx to x.xx	x.xx to x.xx
E2 at 4 hours			
n	x	x	x
Mean (SD, SE)	x.xx (x.xxx, x.xxx)	x.xx (x.xxx, x.xxx)	x.xx (x.xxx, x.xxx)
Median	x.xx	x.xx	x.xx
Minimum to Maximum	x.xx to x.xx	x.xx to x.xx	x.xx to x.xx
E2 at 12 hours			
n	x	x	x
Mean (SD, SE)	x.xx (x.xxx, x.xxx)	x.xx (x.xxx, x.xxx)	x.xx (x.xxx, x.xxx)
Median	x.xx	x.xx	x.xx

Haleon Confidential

CCI

Statistical Analysis Plan Template v7.0

Page 36 of 43

Minimum to Maximum	x.xx to x.xx	x.xx to x.xx	x.xx to x.xx
--------------------	--------------	--------------	--------------

Table 14.3.1, Summary of Adverse Events and Device Incidents Overall and by Treatment Group, Safety Population

	Test (N=XXX)	Reference (N=XXX)	Placebo (N=XXX)	Overall (N=XXX)
Any Adverse Event				n (x.x%)
Any Serious Adverse Event				n (x.x%)
Any Treatment Emergent Adverse Event (TEAE)	n (x.x%)	n (x.x%)	n (x.x%)	n (x.x%)
Any Serious TEAE	n (x.x%)	n (x.x%)	n (x.x%)	n (x.x%)
Any Oral TEAE	n (x.x%)	n (x.x%)	n (x.x%)	n (x.x%)
Any Product Related TEAE	n (x.x%)	n (x.x%)	n (x.x%)	n (x.x%)
Any Device Related AE				n (x.x%)
Any Device Incidents				n (x.x%)

Percentages are based on all subjects in the Safety population according to the study product received.

Haleon Confidential

CCI

Statistical Analysis Plan Template v7.0

Page 38 of 43

Listing 16.2.1, Subject Disposition, Screened Population

ID	Age / Sex / Race / Ethnicity	Visit Dates	Treatment Sequence Group	Analysis population	Completer	Reason for Discontinue	Date of Discontinue
	Age / Female or Male / Race / Ethnicity	V1: Date 1 V2: Date 2 V3: Date 3 V4: Date 4 V5: Date 5 V6: Date 6 V7: Date 7	ABC	ITT / SAF / PP	Yes or No	xxxxxxxxxxxxxxxxxx	DDMMYYYY

A = Test, B = Reference, C= Placebo

Haleon Confidential

CCI

Statistical Analysis Plan Template v7.0

Page 39 of 43

Listing, 16.2.2 Protocol Deviations, ITT Population

ID	Visit Dates	Treatment Sequence Group	Date of PD	Protocol Deviation (PD)	Important PD	Important PD affect efficacy and Visit data exclusion from PP analysis
	V1: Date 1 V2: Date 2 V3: Date 3 V4: Date 4 V5: Date 5 V6: Date 6 V7: Date 7	ABC	DDMMYYYY	xxxxxxxxxxxxxx	Yes or No	Yes or No, Vx

A = Test, B = Reference, C= Placebo

PP = Per-Protocol

Haleon Confidential

CCI

Statistical Analysis Plan Template v7.0

Page 40 of 43

Listing 16.2.3, Exclusions from Efficacy Analysis, ITT Population

ID	Treatment Sequence Group	Study Periods Excluded from PP analysis	Reason for Exclusion
	ABC	P1/P2/P3	XXXXXXXXXXXXXXXXXXXX

A = Test, B = Reference, C= Placebo

Haleon Confidential

CCI

Statistical Analysis Plan Template v7.0

Page 41 of 43

Listing 16.2.7.1, Adverse Events, ITT Population

ID	Visit Dates	Treatment Sequence Group	AE Description	AE Dates Start-Stop	TEAE / Last Study Product Used	Serious/ Severity / Related to Study Product / Oral	Frequency/ Outcome/ Action/ Withdraw from study
	V1: Date 1 V2: Date 2 V3: Date 3 V4: Date 4 V5: Date 5 V6: Date 6 V7: Date 7	ABC	xxxxxxxxxxxxxxxxxxxx	DDMMYYYY- DDMMYYYY	Yes or No, A	Serious or Not Serious / Mild or Moderate or Severe / Related or Not Related / Oral or Not Oral	Xxxx/ Xxxx/ Xxxx/ Yes or No

A = Test, B = Reference, C= Placebo

Haleon Confidential

CCI

Statistical Analysis Plan Template v7.0

Page 42 of 43

Listing 16.2.7.2, Device Incidents, Non-Randomized Subjects

ID	Visit Dates	Treatment Sequence Group	Incident Date	Incident Description	Incident related to AE
	V1: Date 1 V2: Date 2 V3: Date 3 V4: Date 4 V5: Date 5 V6: Date 6 V7: Date 7	ABC	DDMMYYYY	XXXXXXXXXXXXXXXXXX	Yes or No

A = Test, B = Reference, C= Placebo

Haleon Confidential

CCI

Statistical Analysis Plan Template v7.0

Page 43 of 43
